3.16. Interim Analyses and Data Monitoring Committee

The details for the interim analyses and data monitoring committee (DMC) will be provided in the DMC charter.

4. Unblinding Plan

Details of the blinding and unblinding will be provided in the blinding and unblinding plan document for Study GPID.

- 5. Supporting Documentation
- 5.1. Appendix 1: Kansas City Cardiomyopathy Questionnaire Scoring Instructions

The Kansas City Cardiomyopathy Questionnaire Scoring Instructions

There are 10 summary scores within the KCCQ, which are calculated as follows:

1. Physical Limitation

• Code responses to each of Questions 1a-f as follows:

```
Extremely limited = 1
Quite a bit limited = 2
Moderately limited = 3
Slightly limited = 4
Not at all limited = 5
Limited for other reasons or did not do = <missing value>
```

• If at least three of Questions 1a-f are not missing, then compute

```
Physical Limitation Score = 100*[(mean of Questions 1a-f actually answered) - 1]/4 (see footnote at end of this document for explanation of meaning of "actually answered")
```

2. Symptom Stability

• Code the response to Question 2 as follows:

```
Much worse = 1
Slightly worse = 2
Not changed = 3
Slightly better = 4
Much better = 5
I've had no symptoms over the last 2 weeks = 3
```

• If Question 2 is not missing, then compute

```
Symptom Stability Score = 100*[(Question 2) - 1]/4
```

3. Symptom Frequency

• Code responses to Questions 3, 5, 7 and 9 as follows:

```
Question 3
Every morning = 1
3 or more times a week but not every day = 2
1-2 times a week = 3
Less than once a week = 4
Never over the past 2 weeks = 5
```

KCCQ Scoring Instructions / 2

3. Symptom Frequency (cont.)

```
Questions 5 and 7
All of the time = 1
Several times a day = 2
At least once a day = 3
3 or more times a week but not every day = 4
1-2 times a week = 5
Less than once a week = 6
Never over the past 2 weeks = 7

Question 9
Every night = 1
3 or more times a week but not every day = 2
1-2 times a week = 3
Less than once a week = 4
Never over the past 2 weeks = 5
```

• If at least two of Questions 3, 5, 7 and 9 are not missing, then compute:

```
S3 = [(Question 3) - 1]/4

S5 = [(Question 5) - 1]/6

S7 = [(Question 7) - 1]/6

S9 = [(Question 9) - 1]/4
```

Symptom Frequency Score = 100*(mean of S3, S5, S7 and S9)

4. Symptom Burden

• Code responses to each of Questions 4, 6 and 8 as follows:

```
Extremely bothersome = 1
Quite a bit bothersome = 2
Moderately bothersome = 3
Slightly bothersome = 4
Not at all bothersome = 5
I've had no swelling/fatigue/shortness of breath = 5
```

• If at least one of Questions 4, 6 and 8 is not missing, then compute

```
Symptom Burden Score = 100*[(mean of Questions 4, 6 and 8 actually answered) - 1]/4
```

5. Total Symptom Score

```
= mean of the following available summary scores:
Symptom Frequency Score
Symptom Burden Score
```

© Copyright 2000 – 2003 John Spertus MD MPH

Rev. 3/27/01

KCCQ Scoring Instructions / 3

6. Self-Efficacy

• Code responses to Questions 10 and 11 as follows:

Question 10

Not at all sure = 1

Not very sure = 2

Somewhat sure = 3

Mostly sure = 4

Completely sure = 5

Question 11

 $\overline{\text{Do not understand at all}} = 1$

Do not understand very well = 2

Somewhat understand = 3

Mostly understand = 4

Completely understand = 5

• If at least one of Questions 10 and 11 is not missing, then compute

Self-Efficacy Score = 100*[(mean of Questions 10 and 11 actually answered) - 1]/4

7. Quality of Life

• Code responses to Questions 12, 13 and 14 as follows:

Ouestion 12

It has extremely limited my enjoyment of life = 1

It has limited my enjoyment of life quite a bit = 2

It has moderately limited my enjoyment of life = 3

It has slightly limited my enjoyment of life = 4

It has not limited my enjoyment of life at all = 5

Question 13

Not at all satisfied = 1

Mostly dissatisfied = 2

Somewhat satisfied = 3

Mostly satisfied = 4

Completely satisfied = 5

Question 14

I felt that way all of the time = 1

I felt that way most of the time = 2

I occasionally felt that way = 3

I rarely felt that way = 4

I never felt that way = 5

 $\ ^{\ }$ Copyright 2000-2003 John Spertus MD MPH

Rev. 3/27/01

KCCQ Scoring Instructions / 4

7. Quality of Life (cont.)

• If at least one of Questions 12, 13 and 14 is not missing, then compute

Quality of Life Score = 100*[(mean of Questions 12, 13 and 14 actually answered) – 1]/4

8. Social Limitation

• Code responses to each of Questions 15a-d as follows:

```
Severely limited = 1
Limited quite a bit = 2
Moderately limited = 3
Slightly limited = 4
Did not limit at all = 5
Does not apply or did not do for other reasons = < missing value>
```

If at least two of Questions 15a-d are not missing, then compute

Social Limitation Score = 100*[(mean of Questions 15a-d actually answered) - 1]/4

9. Overall Summary Score

= mean of the following available summary scores:

Physical Limitation Score Total Symptom Score Quality of Life Score Social Limitation Score

10. Clinical Summary Score

= mean of the following available summary scores: Physical Limitation Score Total Symptom Score

Note: references to "means of questions actually answered" imply the following.

If there are n questions in a scale, and the subject must answer m to score the scale, but the subject answers only n-i, where $n-i \ge m$, calculate the **mean of those questions** as

```
(sum of the responses to those n-i questions) / (n-i)
(sum of the responses to those n-i questions) / n
```

If doing these calculations seems like too much trouble, consider using one of our tools – available at www.cvoutcomes.org:

- SAS or SPSS code
- Excel spreadsheets
- Web data services

© Copyright 2000 - 2003 John Spertus MD MPH

Rev. 3/27/01

Question No.	Domain	Question	Response
1a	Physical limitation	How much are you limited by heart failure (shortness of breath or fatigue) in dressing yourself over the past 2 weeks?	
1b	Physical limitation	How much are you limited by heart failure (shortness of breath or fatigue) in showering/bathing over the past 2 weeks?	
1c	Physical limitation	How much are you limited by heart failure (shortness of breath or fatigue) in walking 1 block on level ground over the past 2 weeks?	1: Extremely limited 2: Quite a bit limited 3: Moderately limited 4: Slightly limited
1d	Physical limitation	How much are you limited by heart failure (shortness of breath or fatigue) in doing yard work, housework or carrying groceries over the past 2 weeks?	5: Not at all limited 0: Limited for other reasons or did not do the activity
1e	Physical limitation	How much are you limited by heart failure (shortness of breath or fatigue) in climbing a flight of stairs without stopping over the past 2 weeks?	
1f	Physical limitation	How much are you limited by heart failure (shortness of breath or fatigue) in hurrying or jogging over the past 2 weeks?	

Question No.	Domain	Question	Response
	Symptom Stability		1: Much worse
		Compared with 2 weeks ago,	2: Slightly worse
		have your symptoms of heart failure (shortness of breath,	3: Not changed
2		fatigue, or ankle swelling)	4: Slightly better
		changed?	5: Much better
			3.0: I had no symptoms over the last 2 weeks
	Symptom	Over the past 2 weeks, how many times did you have swelling in your feet, ankles or legs when	1: Every morning
	Frequency		2: 3 or more times a week, but not every day
3			3: 1-2 times a week
		you woke up in the morning?	4: Less than once a week
			5: Never over the past 2 weeks
	Symptom Burden		1: Extremely bothersome
4		Over the past 2 weeks, how much has swelling in your feet, ankles or legs bothered you?	2: Quite a bit bothersome
			3: Moderately bothersome
			4: Slightly bothersome
			5: Not at all bothersome
			5.0: I've had no swelling

Question No.	Domain	Question	Response
	Symptom		1: All of the time,
	Frequency		2: Several times per day
			3: At least once a day
5		Over the past 2 weeks, on average, how many times has fatigue limited your ability to do	4: 3 or more times per week but not every day
		what you want?	5: 1-2 times per week
			6: Less than once a week
			7: Never over the past 2 weeks
	Symptom Burden		1: Extremely bothersome
			2: Quite a bit bothersome
6		Over the past 2 weeks, how much has your fatigue bothered you?	3: Moderately bothersome
6			4: Slightly bothersome
			5: Not at all bothersome
			5.0: I've had no fatigue
	Symptom	Over the past 2 weeks, on average, how many times has shortness of breath limited your ability to do what you wanted?	1: All of the time
	Frequency		2: Several times per day
			3: At least once a day
7			4: 3 or more times per week but not every day
			5: 1-2 times per week
			6: Less than once a week
			7: Never over the past 2 weeks

Question No.	Domain	Question	Response
	Symptom Burden		1: Extremely bothersome
			2: Quite a bit bothersome
		Over the past 2 weeks, how much	3: Moderately bothersome
8		has your shortness of breath	4: Slightly bothersome
		bothered you?	5: Not at all bothersome
			5.0: I've had no shortness of breath
	Symptom		1: Every night
	Frequency	Over the past 2 weeks, on average, how many times have you been forced to sleep sitting up in a chair or with at least 3 pillows to prop you up because of shortness of breath?	2: 3 or more times a week, but not every day
9			3: 1-2 times a week
			4: Less than once a week
			5: Never over the past 2 weeks
	Self-efficacy	Heart failure symptoms can worsen for a number of reasons. How sure are you that you know	1: Not at all sure
			2: Not very sure
10			3: Somewhat sure
		what to do, or whom to call, if your heart failure gets worse?	4: Mostly sure
		, ,	5: Completely sure
	Self-efficacy		1: Do not understand at all
11		How well do you understand what things you are able to do to	2: Do not understand very well
		keep your heart failure symptoms	3: Somewhat understand
		from getting worse?	4: Mostly understand
			5: Completely understand

Question No.	Domain	Question	Response
	Quality of Life		1: It has extremely limited my enjoyment of life
			2: It has limited my enjoyment of life quite a bit
12		Over the past 2 weeks, how much has your heart failure limited your enjoyment of life?	3: It has moderately limited my enjoyment of life
			4: It has slightly limited my enjoyment of life
			5: It has not limited my enjoyment of life at all
	Quality of Life		1: Not at all satisfied
		If you had to spend the rest of your life with your heart failure the way it is right now, how would you feel about this?	2: Mostly dissatisfied
13			3: Somewhat satisfied
			4: Mostly satisfied
			5: Completely satisfied
14	Quality of Life	Over the past 2 weeks, how often have you felt discouraged or	1: I felt that way all of the time
			2: I felt that way most of the time
		down in the dumps because of your heart failure?	3: I occasionally felt that way
			4: I rarely felt that way
			5: I never felt that way

Question No.	Domain	Question	Response
15a	Social Limitation	How much have your heart failure limited your participation in hobbies, recreational activities over the past 2 weeks?	1: Severely limited
15b	Social Limitation	How much have your heart failure limited your participation in working or doing household chores over the past 2 weeks?	2: Limited quite a bit3: Moderately limited4: Slightly limited5: Did not limited at all6: Does not apply or did not do for other reasons
15c	Social Limitation	How much have your heart failure limited your participation in visiting family or friends out of your home over the past 2 weeks?	
15d	Social Limitation	How much have your heart failure limited your participation in intimate relationships with loved ones over the past 2 weeks?	

5.2. Appendix 2: Search Criteria for Special Safety Topics

Diabetic Retinopathy Complications

Diabetic retinopathy complications will be identified using the following MedDRA PTs:

Duofound Toum	Codo
Preferred Term	Code
Arteriosclerotic retinopathy	10063452
Blindness	10005169
Blindness transient	10005184
Blindness unilateral	10005186
Cystoid macular oedema	10058202
Diabetic blindness	10012646
Diabetic eye disease	10012661
Diabetic retinal oedema	10012688
Diabetic retinopathy	10012689
Diabetic uveitis	10012692
Exudative retinopathy	10015901
Eye laser surgery	10057105
Fundoscopy	10017519
Fundoscopy abnormal	10017520
Intra-ocular injection	10057098
Macular detachment	10075873
Macular oedema	10025415
Maculopathy	10025425
Non-proliferative retinopathy	10081568
Phacotrabeculectomy	10059276
Retinal collateral vessels	10077911
Retinal cryoablation	10074908
Retinal detachment	10038848
Retinal exudates	10038862
Retinal haemorrhage	10038867
Retinal laser coagulation	10038873
Retinal neovascularisation	10055666
Retinal oedema	10038886
Retinal operation	10062107
Retinal thickening	10077890
Retinal vascular disorder	10077890
Retinal vascular occlusion	
	10038903
Retinal vein occlusion	10038907
Retinopathy	10038923

Preferred Term	Code
Retinopathy haemorrhagic	10051447
Retinopathy hypertensive	10038926
Retinopathy proliferative	10038934
Sudden visual loss	10042441
Vision blurred	10047513
Visual acuity reduced	10047531
Visual acuity reduced transiently	10047532
Visual impairment	10047571
Vitrectomy	10047644

Arrhythmias and Cardiac Conduction Disorders

TE arrhythmias, arrhythmias, and cardiac conduction disorders will be considered as AESI. Cardiovascular events will include clinically relevant rhythm and conduction disorders. TE arrhythmias and cardiac conduction disorders events will be included using the MedDRA PT contained in any of the following SMQs:

- 1) Arrhythmias:
 - For symptoms: *Arrhythmia related investigations, signs and symptoms* SMQ (20000051), narrow and broad terms
 - For supraventricular arrhythmias: in *Cardiac arrhythmia* SMQ, under the tachyarrhythmia sub SMQ
 - o Supraventricular tachyarrhythmia SMQ (20000057), broad and narrow terms
 - o *Tachyarrhythmia terms, nonspecific* SMQ (20000164), narrow terms only, and
 - o Ventricular tachyarrhythmia SMQ (20000058), narrow terms only.
- 2) Cardiac Conduction Disorders
 - Conduction defects SMQ (2000056), narrow terms only, and
 - Cardiac conduction disorders High Level Term (HLT; 10000032), all PTs.

Injection Site Reactions

TE ISRs will be summarized by treatment using the MedDRA PT in any of the following:

- HLT of *Injection site reaction*
- HLT of *Administration site reaction*
- HLT of *Infusion Site Reactions*

Acute Gallbladder Disease

All events of TEAE biliary colic, cholecystitis, or other suspected events related to gallbladder disease will be summarized by treatment groups by PT with decreasing frequency under following SMQs:

- narrow PTs in Gallbladder related disorders SMQ (20000124)
- narrow PTs in Biliary tract disorders SMQ (20000125), and
- narrow PTs in Gallstone related disorders SMQ (20000127).

Hepatic Treatment-Emergent Adverse Events

TE potentially drug-related hepatic disorders will be summarized by treatment using the MedDRA PTs contained in any of the following SMQs:

- broad and narrow terms in the *Liver related investigations, signs and symptoms* SMQ (20000008)
- broad and narrow terms in the *Cholestasis and jaundice of hepatic origin* SMQ (20000009)
- broad and narrow terms in the *Hepatitis non-infections* SMQ (20000010)
- broad and narrow terms in the *Hepatic failure, fibrosis and cirrhosis and other liver damage* SMQ (20000013), and
- narrow terms in the *Liver-related coagulation and bleeding disturbances* SMQ (20000015).

Metabolic Acidosis

Metabolic acidosis will be identified using the following MedDRA PTs:

Preferred Term	Code
Blood ketone body	10057593
Blood ketone body increased	10057594
Blood ketone body present	10057598
Diabetic ketoacidosis	10012671
Diabetic ketoacidotic hyperglycaemic coma	10012672
Diabetic ketosis	10012673
Euglycaemic diabetic ketoacidosis	10080061
Ketoacidosis	10023379
Ketonuria	10023388
Ketosis	10023391
Lactic acidosis	10023676
Urine ketone body	10059222
Urine ketone body present	10057597

Hypotension, Orthostatic Hypotension, and Syncope

Hypotension, orthostatic hypotension, and syncope will identified using the following MedDRA PTs:

Preferred Term	Code
Diastolic hypotension	10066077
Hypotension	10021097
Hypotensive crisis	10083659
Orthostatic hypotension	10031127
Blood pressure ambulatory decreased	10005731
Blood pressure decreased	10005734
Blood pressure diastolic decreased	10005737
Blood pressure orthostatic decreased	10053356
Blood pressure systolic decreased	10005758
Mean arterial pressure decreased	10026983
Blood pressure orthostatic	10053352
Dizziness	10013573
Presyncope	10036653
Syncope	10042772
Drop attacks	10013643
Loss of consciousness	10024855

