- Any clinically significant abnormal laboratory findings or other abnormal safety assessments which are associated with the underlying disease, unless judged by the investigator to be more severe than expected for the participant's condition.
- The disease/disorder being studied or expected progression, signs, or symptoms of the disease/disorder being studied, unless more severe than expected for the participant's condition.
- Medical or surgical procedure (for example, endoscopy, appendectomy): the condition that leads to the procedure is the AE.
- Situations in which an untoward medical occurrence did not occur (social and/or convenience admission to a hospital).
- Anticipated day-to-day fluctuations of preexisting disease(s) or condition(s) present or detected at the start of the study that do not worsen.

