3.14.3.2. Diabetic Retinopathy Complications

Results of the baseline dilated fundoscopic exam will be summarized by treatment. Any TEAE suspected of worsening retinopathy triggers a follow-up dilated fundoscopic exam. A summary of TEAEs suspected of worsening retinopathy will be summarized by treatment and PT. Severe or serious AEs will be classified as AESI and a listing provided.

A complete list of PTs for inclusion in the above analyses is available in Appendix 2, Section 5.2.

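### The closed term list for diabetic retinopathy complications names the operation Vitrectomy but no vitreous haemorrhage, so a bleed reported under its own name drops out of that summary and its AESI listing

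*SAP*

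**What the plan says.** SAP 3.14.3.2 plans two adverse-event displays for this topic besides the baseline fundoscopy results.

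- The first is a table: "A summary of TEAEs suspected of worsening retinopathy will be summarized by treatment and PT".
- The second is the special-interest listing: "Severe or serious AEs will be classified as AESI and a listing provided".

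The same section fixes which terms feed them: "A complete list of PTs for inclusion in the above analyses is available in Appendix 2, Section 5.2". Appendix 2 then states "Diabetic retinopathy complications will be identified using the following MedDRA PTs" and gives 43 named terms. No standardized query, high-level term or open-ended wording is added.

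Protocol 10.3.1, under events that do not meet the AE definition, says: "Medical or surgical procedure (for example, endoscopy, appendectomy): the condition that leads to the procedure is the AE". Protocol 10.3.4 asks for the diagnosis in preference to signs and symptoms where possible. Protocol 9.4.5 has events coded from the term actually reported. Protocol 8.3.3 does not name retinopathy among its AESI, but it leaves the details of AESI definitions to the SAP. The Appendix 2 list therefore decides what this topic contains.

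**The concern.** By listing Vitrectomy, the sponsor treated that operation as relevant to retinopathy complications. The protocol, however, tells sites not to report an operation as the event but to report the condition behind it. If that condition is a bleed into the vitreous, the list has no term for it. The search would then look for a term that sites are told not to use and pass over the one they are told to use.

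Nothing else in the topic would fill the gap. Several other topics in Appendix 2 (arrhythmias, injection site reactions, gallbladder disease, hepatic events) are searched by standardized queries or high-level terms, where a term that nobody thought of may still be caught by the grouping. Here the named terms stand alone. Dilated fundoscopy does not help either. The Schedule of Activities places it at screening, for participants with type 2 diabetes who lack a recent evaluable examination. After that it is done only when an adverse event suggests worsening retinopathy.

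What is at stake is how complete one safety-topic table and its AESI listing are.

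**Working it through.** The plan gives no figure on this point to reproduce. The check is a count of the list, followed by a trace of one event through the reporting and selection rules.

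**Step 1: count the list (SAP 5.2, Diabetic Retinopathy Complications).**

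- Terms in total: 43, in alphabetical order.
- Terms that concern the vitreous: 1, *Vitrectomy*, in the last row.
- Terms that name bleeding: 2, "Retinal haemorrhage" and "Retinopathy haemorrhagic". Both refer to the retina or to retinopathy.
- Terms that name vitreous haemorrhage: 0.
- Procedure or investigation terms: 9 (Eye laser surgery, Fundoscopy, Fundoscopy abnormal, Intra-ocular injection, Phacotrabeculectomy, Retinal cryoablation, Retinal laser coagulation, Retinal operation, Vitrectomy). That leaves 43 − 9 = 34 condition or symptom terms, none of them a vitreous bleed.

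**Step 2: trace a treatment-emergent vitreous bleed through the rules.**

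| How the site reports it | Retinopathy summary (SAP 3.14.3.2) | AESI listing, if severe or serious | Elsewhere |
|---|---|---|---|
| The bleed under its own name, no other listed term | Not selected | Not selected | General TEAE tables (SAP 3.14.1.1). If serious, also the SAE table and listing (3.14.1.4) and a narrative (3.14.2) |
| The bleed plus a listed condition, such as Diabetic retinopathy | Participant selected through the listed term | Selected if the listed event is severe or serious | Same |
| The operation, Vitrectomy, against Protocol 10.3.1 | Selected | Selected | Same |
| A symptom only, such as Vision blurred, although 10.3.4 prefers the diagnosis | Selected | Selected | Same |

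Only the first row is lost to the topic. It is also a row that a site following Protocol 10.3.1 and 10.3.4 can readily produce.

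**Step 3: what the trace assumes.** A vitreous bleed must code to a preferred term outside the 43. The documents do not show the MedDRA hierarchy, so this must be checked in version 27.0, the version named in SAP 3.8. The absence of the term must also be confirmed in the PDF. A vitreous haemorrhage term would sort directly after the last row, and the text I worked from was extracted by program and shows a code repeated on two rows. That text has no sign of a cut at the end of the list: the next heading follows immediately.

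**The case against.** The strongest reply is that the event is not lost. SAP 3.14.1.1 tabulates every treatment-emergent event by preferred term with a treatment comparison, and serious events are also tabulated, listed and narrated. A reader might infer from the gap that a vitreous bleed is never counted, or that a zero or balanced retinopathy count would be falsely reassuring. The documents do not support either inference. The omission is confined to one topic table and its AESI listing, and nothing shows how many events, if any, would be affected.

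A second reply is that the investigator may name the underlying disease. Diabetic retinopathy, Retinopathy proliferative, Retinal neovascularisation and Retinal haemorrhage are all listed. A suspected worsening also prompts a fundoscopic examination, which may supply such a term. This stands, and it is why the point is limited to participants with no other listed term. It does not close the gap, because capture then depends on a second term being reported.

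A third reply is that the lists were aligned with a program-level plan (SAP revision summary) that is not available here, so the omission may be deliberate. That is possible, but neither document gives a reason. The documents also do not say that a vitreous bleed is a complication of diabetic retinopathy; the support within them is that the list itself includes Vitrectomy.

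Finally, coded data will exist and SAP 3.2 allows additional analyses, so the omission could be repaired later. That lowers the priority. It is still better to fix a search list before treatment assignments are known.

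**Conclusion.** The point holds in limited form. Following the list as written, a vitreous bleed reported under its own name, with no other listed term for that participant, is left out of the retinopathy summary and, if severe or serious, out of the AESI listing. This rests on such a bleed coding to its own preferred term and on the PDF table ending at Vitrectomy.

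The size cannot be estimated. Protocol 2.2 works with 40% to 50% type 2 diabetes, which for 700 participants is 700 × 0.40 = 280 to 700 × 0.50 = 350. A reader might treat all of these as at risk and multiply by an event rate. The documents give no such rate and no share that would be severe or serious. Exclusion criterion 25 also removes a history of proliferative retinopathy or maculopathy, and severe non-proliferative disease in need of acute treatment. The number is therefore likely to be small, although other non-proliferative disease remains eligible.

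It would also go too far to infer that the other listed eye procedures lack their leading conditions. No second missing condition was identified, and unused procedure terms do no harm.

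No primary, key secondary or multiplicity-controlled result is affected. This is a cheap improvement of low priority.

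**What to change.** Before unblinding, add the vitreous haemorrhage preferred term or terms to the diabetic retinopathy list in SAP Appendix 2. First confirm the terms and codes in MedDRA 27.0, and confirm in the PDF table that they are not already there.

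The cost is a small edit to a search list. No new data, site action or change to any other analysis is needed. The downside is that an occasional vitreous bleed with no link to diabetes would also be counted. The list already accepts that loss of specificity for Retinal detachment and Retinal vein occlusion.
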